### **5.3. Group Assignment and Randomization**

A participant's AHI estimate from the first clinic visit determines whether she is randomized, assigned to the control group for observation only, or withdrawn from the study. Participants with an AHI estimate below 5 are assigned to the control group. They are not randomized. Participants with an AHI estimate of 50 or higher are referred to a sleep specialist and withdrawn from the study. They are not randomized. Participants with an AHI estimate 5-49 who agree to randomization are randomized by the Study Coordinator to CPAP or Sleep Hygiene, based on a system developed by the DCC (see below).

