Rationale:

Currently our study, in part, consists of a randomized controlled trial of Auto-CPAP vs. Sham CPAP in pregnancy. As of 2/14/17, we have screened 309 participants, enrolled 228, randomized 43 to auto-CPAP or sham CPAP, and assigned 96 to the control group for observation only. We are very pleased with our study recruitment and data collection processes. We are recruiting on schedule and have excellent retention. The over-arching goals of my study were to provide mechanistic insights on how SDB impacts pregnancy and to provide preliminary/feasibility data to inform the practical and scientific aspects of a CPAP and pregnancy trial. For the latter, I would like to continue to make iterative changes to the protocol to understand best practices to optimize CPAP use in pregnancy as part of a clinical trial. To improve compliance to CPAP among randomized subjects, we have added a monetary incentive and we have demonstrated a positive effect from this modification, but, given recent data from other sleep cohorts, I remain wary about how having a sham arm may be hindering compliance. My co-investigators and I are requesting approval for this modification because we believe that it will enhance the scientific value of our study data. The CPAP trial component of our study (Aims 2 and 3 outlined below) is a pilot study not designed to definitively determine effectiveness, but rather determine the feasibility and acceptability of a CPAP trial in pregnancy and see if a treatment effect is possible to consider for a larger study. To that end, we strongly believe that any modification that leads to increased adherence to treatment will be of great value.

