In summary, analyses would begin by describing the baseline characteristics by randomly assigned treatment group. Either parametric (t-test) or nonparametric (Wilcoxon test) analyses would be used to compare continuous characteristics and chi-square tests would be used to compare discrete characteristics across randomly assigned treatment groups. The analyses would be carried out based on intention to treat, but exploratory analyses would be conducted on the per protocol subgroup. The treatment effects of sleep hygiene vs. active CPAP on the vector of cardiovascular risk factors would be compared with multivariate analysis of variance (MANOVA). If differences in baseline characteristics are observed, the characteristics would be included in the MANOVA to control for the potential confounding effects. This analytic plan would be repeated in the per-protocol subgroup. The MANOVA model would be fit with main effects for treatment group and an indicator of the level of compliance as well as the two-way interaction. Additionally, ANOVA and X^2 analyses would be used to examine intergroup differences between Time 1 and Time 2 assessments among all the groups. The assumptions of all analyses (e.g., normality of residuals) would be investigated. If assumptions are violated, transformations of the data would be investigated. If adequate transformations cannot be identified, nonparametric approaches would be utilized.

The revised design would have two impacts on the study design. First, would be a reduction in power of the first comparison. The second would be the size of the effect that can be estimated in the modified design analysis; the detectable effect size would be larger (1.52, assuming 80% power, a type I error rate of 0.05, a two-sided alternative hypothesis, with four outcomes variables in the MANOVA). However, given that Aim 2 and 3 are designed as a pilot study, the size of the effect should not be a concern since the goal of the study is not to definitively determine effectiveness, but rather determine the feasibility of a CPAP trial in pregnancy and see if a treatment effect is possible to consider for a larger study. To that end, any modification that leads to increased adherence to treatment would be of great value to this study, as well as future investigations.

D. Budget

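### The Time 1–Time 2 comparison does not define its groups, and no Aim 2 analysis commits to adjusting for the outcome's Visit 1 value

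*SAP*

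**What the plan says.** The SAP's section C sets out the revised plan for Aims 2 and 3 in one paragraph.

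- **Analysis set.** "The analyses would be carried out based on intention to treat", with per-protocol analyses exploratory.
- **Treatment effect.** "The treatment effects of sleep hygiene vs. active CPAP on the vector of cardiovascular risk factors would be compared with multivariate analysis of variance (MANOVA").
- **Covariates.** "If differences in baseline characteristics are observed, the characteristics would be included in the MANOVA". The rule is written for the MANOVA only, and the outcome's own Visit 1 value is not named.
- **The sentence at issue.** As an addition to the MANOVA, ANOVA and chi-square tests are to examine "intergroup differences between Time 1 and Time 2 assessments among all the groups". No covariate, contrast or handling of pairing is given.

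The paragraph opens by "describing the baseline characteristics by randomly assigned treatment group" and uses the same expression again for the baseline tests. It changes to a wider term only in the Time 1–Time 2 sentence.

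The control group is formed by a threshold: "Participants with an AHI estimate below 5 are assigned to the control group. They are not randomized" (Protocol, SOAP2 manual, 5.3; the SOAP1 manual, 5.3, says the same). Controls attend the same two visits as everyone else (both manuals, 5.2). By 14 February 2017 the study had "assigned 96 to the control group for observation only" and had randomised 43 women (SAP, Rationale). Section B plans 45 women randomised to active or sham CPAP, then 36 to active CPAP or sleep hygiene (18 each).

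**The concern.** The Time 1–Time 2 sentence is the only one in the SAP that explicitly uses both visits, and its result cannot be interpreted until its terms are fixed.

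Four groups attend both visits: active CPAP, sham, sleep hygiene and controls without sleep-disordered breathing (SDB). A test across all four asks whether any group differs. It can be significant only because women without SDB follow a different course through pregnancy, which is close to the study's own central hypothesis. Such a result could be mistaken for the treatment signal that the pilot is meant to look for.

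The second issue is precision. The Visit 1 value of an Aim 2 outcome is likely to be its best available predictor at Visit 2, yet nothing in the plan guarantees its use. The MANOVA rule brings in baseline variables only after a difference has been seen. A strongly prognostic Visit 1 value that happens to be balanced would be left out. With 18 women per arm in the second phase, that is a needless loss.

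**Working it through.** **1. The plan's own figure.** The SAP gives a detectable effect of 1.52 (80% power, two-sided 0.05, four outcomes). A two-group MANOVA is Hotelling's T². With 18 and 18 the F statistic has 4 and 18 + 18 − 4 − 1 = 31 degrees of freedom, and the noncentrality is (18 × 18/36) × D² = 9D². Power of 80% needs D² = 1.54 (D = 1.24), and D² = 1.52 gives 79.3%. So 1.52 reproduces as a squared Mahalanobis distance for the second phase alone. Read as D, it would give 94.1% power. The SAP does not name the metric, so this match is an inference. The Time 1–Time 2 sentence does not affect the figure.

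**2. Value of the Visit 1 measurement.** Let ρ be the correlation between visits, with a common SD. Relative to the variance of a single Visit 2 value, the arm difference has variance 1 (Visit 2 only), 2(1 − ρ) (change score) or 1 − ρ² (ANCOVA). The documents give no ρ, so a range is assumed.

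| ρ (assumed) | Visit 2 only | Change | ANCOVA | ANCOVA saving vs change | Saving vs Visit 2 only |
|---|---|---|---|---|---|
| 0.3 | 1 | 1.40 | 0.91 | 35% | 9% |
| 0.5 | 1 | 1.00 | 0.75 | 25% | 25% |
| 0.7 | 1 | 0.60 | 0.51 | 15% | 49% |

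The saving against change is 1 − (1 + ρ)/2 = (1 − ρ)/2, so it is 10% at ρ = 0.8. The last column matters if the unadjusted analysis uses Visit 2 values, which the SAP leaves open.

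**3. At 18 per arm.** For one outcome, an unadjusted two-sample t-test detects 0.96 SD (80% power, two-sided 0.05). Multiplying by the square root of each variance:

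| ρ | Change | ANCOVA | n per arm for an illustrative 0.8 SD, change vs ANCOVA |
|---|---|---|---|
| 0.3 | 0.96 × √1.40 = 1.14 | 0.96 × √0.91 = 0.92 | 35 vs 23 |
| 0.5 | 0.96 × √1.00 = 0.96 | 0.96 × √0.75 = 0.83 | 25 vs 19 |
| 0.7 | 0.96 × √0.60 = 0.75 | 0.96 × √0.51 = 0.69 | 15 vs 13 |

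These figures ignore the single degree of freedom that ANCOVA spends. For the four-outcome MANOVA, four Visit 1 covariates reduce the denominator degrees of freedom from 31 to 27. The required D² on the residual scale is then 1.58. Multiplying by 1 − ρ² gives about 1.44, 1.18 and 0.8 at ρ = 0.3, 0.5 and 0.7, against 1.54 with Visit 2 values unadjusted. This assumes the same ρ for every outcome.

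**4. Wide reading: controls included.** A one-way ANOVA on change was simulated 20,000 times with no CPAP effect. Assumed group sizes were 40 CPAP (22 + 18), 23 sham, 18 hygiene and 96 controls, with ρ = 0.5. The split of the first 45 and the control shifts are assumptions.

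| Shift in controls' mean change | Four-group test rejects | Randomised arms only |
|---|---|---|
| 0 | 5% | 5% |
| 0.2 SD | 17% | 5% |
| 0.3 SD | 35% | 5% |
| 0.5 SD | 79% | 5% |

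The four-group test is a valid test of whether all groups are equal. It is not a test of CPAP.

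**5. Narrow reading: randomised women only.** The first 45 were randomised between active and sham under blinding, and the next 36 between active and hygiene without it. CPAP against sham, and CPAP against hygiene, are each protected by randomisation only within their own phase. Sham against hygiene is not protected at all. A single test across the arms with no phase term mixes these.

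**The case against.** The strongest reply is that the treatment effect is not assigned to this sentence. It goes to an intention-to-treat MANOVA between randomised arms, and the Time 1–Time 2 tests are an addition. That stands. A reader might infer that the plan contains no randomised contrast; it does. The SAP also discusses the power of the first comparison apart from the modified design, which suggests that comparisons by phase are intended.

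Some further inferences are tempting and are not supported:

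- **That controls are certainly included.** The change of terms, the shared visits and Aim 3's comparison of women with and without SDB make this the more natural reading. The text does not say so.
- **That change scores are certainly analysed.** The sentence could also mean unpaired tests at each visit. Neither version pre-specifies the Visit 1 covariate.
- **That regression to the mean drives the result.** Controls are selected on AHI, so it acts directly on AHI. The primary measures in the SAP's Table 1 (uterine artery pulsatility index, sFLT/PlGF ratio, HOMA-IR) are not selection variables. They would be affected only through a link with AHI measurement error, which the documents do not quantify.
- **That comparing controls is wrong in itself.** Aim 3 legitimately does so.

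The covariate rule could be read broadly enough to cover Visit 1 outcome values, but it would remain conditional on an observed difference. The manuals refer to a separate Protocol for statistical models, and the SAP to an original application. Definitions may sit there, but neither is among the documents reviewed. Finally, these aims are a pilot. That excuses low power, but it does not make an undefined test interpretable.

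**Conclusion.** The point holds in a limited form. The supplementary analysis is undefined, and on either reading it is not a clean randomised comparison of CPAP with its comparator. Separately, no analysis described for Aim 2 commits to the outcome's Visit 1 value as a covariate.

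The precision forgone is a variance reduction of 15% to 35% against change scores for ρ from 0.7 to 0.3. At ρ = 0.5 and 18 per arm, the detectable difference would fall from 0.96 to 0.83 SD. This rests on an assumed correlation and equal SDs at the two visits. The rejection rates of 17% to 79% apply only if controls are included and their mean change differs by 0.2 to 0.5 SD. They illustrate how the test could mislead and are not an estimate for this study.

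The MANOVA of hygiene against CPAP remains a randomised contrast, and the stated 1.52 is unaffected.

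**What to change.** Replace the Time 1–Time 2 sentence with text to this effect:

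- **Definitions.** State that Time 1 and Time 2 are Clinic Visits 1 and 2, and list the groups and the measures in each comparison.
- **Randomised contrast, Aim 2.** For measures taken at both visits (such as uterine artery pulsatility index, sFLT/PlGF ratio and HOMA-IR), compare Visit 2 values between CPAP and its concurrent comparator within each phase. Use ANCOVA or MANCOVA with the Visit 1 value always included, whatever the observed balance. Report the difference and its 95% CI. Include a phase term if the phases are ever combined.
- **Controls.** Report any comparison with the AHI <5 group separately and label it observational.
- **Scope.** Exclude Aim 3's placental profile, which is obtained at delivery. Apply Visit 1 adjustment to a categorical measure only if that measure is recorded at both visits.

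The cost is SAP wording and one degree of freedom per outcome model (four in the four-outcome MANCOVA). No extra visit or assay is needed, because both visits are already scheduled. When the modification was requested, the 36 women of the second phase had still to be randomised, so the rule could be fixed before their data existed.
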